9.3.2 Pharmacokinetic Statistical Methodology

PK parameters will be evaluated to estimate the relative bioavailability of Test Formulation 1 and Test Formulation 2 compared to the commercial formulation (Reference).

Log-transformed C_{max} , $AUC(0-\infty)$ and $AUC(0-t_{last})$ will be evaluated in a linear mixed-effects model with a fixed effect for formulation and a random effect for subject. The treatment differences will be back-transformed to present the ratios of geometric means and the corresponding 90% CI.

Example SAS code:

```
proc mixed data=xxx;  
  by parameter;  
  class formulation subject;  
  model log_pk = formulation / residual;  
  lsmeans formulation / alpha=0.1 cl pdiff;  
  random intercept / subject=subject;  
  ods output lsmeans=lsmeans;  
  ods output diffs=diffs;  
run;
```

The t_{max} will be analyzed using a Wilcoxon rank sum test. Estimates of the median difference based on the observed medians, 90% CIs and p-values from the Wilcoxon rank sum test will be calculated.

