Up to 99 subjects may be enrolled so that 78 subjects (26 in each treatment arm) complete the study.

Statistical Analysis:

Pharmacokinetic parameters will be evaluated to estimate relative bioavailability. Log-transformed C_{max} and AUC parameters will be evaluated in a linear mixed-effects model with fixed effects for formulation, and a random effect for subject. The treatment differences will be back-transformed to present the ratios of geometric means and the corresponding 90% CI.

The t_{max} will be analyzed using a Wilcoxon rank sum test. Estimates of the median difference based on the observed medians, 90% CIs and p-values from the Wilcoxon rank sum test will be calculated.

Safety parameters will be listed and summarized using standard descriptive statistics, where possible. Injection-site assessments, including induration, swelling, pruritis, bleeding/bruising, and erythema/redness, will also be assessed. The parameters will be listed and summarized using descriptive statistics. Suicidal ideation and/or behavior and self-injurious behavior with no suicidal intent, based on the C-SSRS, will be listed by subject. HADS item scores will be listed for subjects with HADS depression subscale ≥ 11 at any time. VAS pain score will be summarized using standard descriptive statistics. In addition, the severity of pain will be categorized by VAS pain score as: mild pain (≤ 30), moderate pain (> 30 and ≤ 70), and severe pain (> 70). The number and percentage of the subjects in each pain severity category will be summarized by formulation and time point.

The frequency and percentage of subjects with preexisting anti-drug antibodies (ADA) and with treatment-emergent ADA (TE ADA) to ixekizumab will be tabulated. Treatment-emergent ADAs are defined as those with a titer 2-fold (1 dilution) greater than the minimum required dilution if no ADAs were detected at baseline (treatment-induced ADA) or those with a 4-fold (2 dilutions) increase in titer compared to baseline if ADAs were detected at baseline (treatment-boosted ADA). For the TE ADA+ subjects the distribution of maximum titers will be described. The frequency of neutralizing antibodies will also be tabulated in TE ADA+ subjects.

Additional analysis will be performed if warranted upon review of the data.

2. Schedule of Activities

Study Schedule Protocol I1F-MC-RHCT

Procedure	Screening	Days																Comments	

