5.1. Overall Design

Study IIF-MC-RHCT is a Phase 1, subject-blind, 3-arm, randomized, parallel-design study in healthy subjects.

All subjects will be screened within 28 days prior to enrollment. Eligible subjects will be admitted to the clinical research unit (CRU) on Day -1 and randomized 1:1:1 to 1 of 3 possible treatments. On Day 1, subjects will receive a single SC dose of one of the following treatments, according to the randomization schedule:

- 80 mg ixekizumab Commercial Formulation (Reference)
- 80 mg ixekizumab Test Formulation 1
- 80 mg ixekizumab Test Formulation 2

Subjects may be allowed to leave the CRU after completing the 4-hour safety assessments on Day 1, at the investigator's discretion, and will return for pharmacokinetic (PK) and immunogenicity sampling and safety assessments at predefined times up to 12 weeks postdose. Subjects will be monitored for safety between outpatient visits by way of telephone assessment.

Safety and tolerability will be assessed by clinical laboratory tests, vital sign measurements, temperature, recording of AEs, physical examination (PE)/medical assessments, Columbia Suicide Severity Rating Scale (C-SSRS), immunogenicity, and injection-site assessments. Pain assessments will be made using an injection-site visual analog scale (VAS).

Study governance considerations are described in detail in [Appendix 3](#).

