5.4. Scientific Rationale for Study Design

Conducting the study in healthy subjects mitigates the potential confounding effects of the disease state and concomitant medications in patients. A population of healthy subjects is frequently used in the assessment of the relative bioavailability of both small and large molecules.

Single doses of ixekizumab and the PK sampling time points have been selected to generate PK profiles sufficient to fulfill the study objectives.

A parallel-group design is chosen because a crossover design is impractical for ixekizumab, which has a half-life of approximately 13 days. Additionally, a crossover study could confound PK data if subjects develop neutralizing antidrug antibodies (ADAs).

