7. SAMPLE SIZE JUSTIFICATION

Up to 99 subjects may be enrolled to ensure that 78 subjects (26 for each treatment) complete the study.

Subjects who are randomized but not administered treatment may be replaced to ensure that 78 subjects (26 for each treatment) complete the study.

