9.4.8 Injection-Site Pain

Visual analog scale (VAS) pain score will be summarized using standard descriptive statistics. In addition, the severity of pain will be categorized by VAS pain score as: mild pain (≤ 30), moderate pain (>30 and ≤ 70), and severe pain (>70). The number and percentage of the subjects in each pain severity category will be summarized by formulation and time point.

A mixed model for the repeating measures analysis model will be used to analyze the continuous injection-site pain VAS score. The model will include formulation and time post injection (0, 10, 20, 30, and 60 minutes) and formulation by time as fixed factors. The covariance

structure of the model will be unstructured. Other covariance matrices may be explored if needed. The Kenward-Roger method will be used to estimate the denominator degrees of freedom. Type III sums of squares for the least squares (LS) means will be used for the statistical comparison; the treatment differences along with their corresponding 95% CIs will also be reported.

[REDACTED]

9.4.9 Columbia-Suicide Severity Rating Scale (C-SSRS) / Self-Harm Supplement / Hospital Anxiety Depression Scale (HADS)

Given that few or no suicidal ideation or behaviours are anticipated, a listing of C-SSRS data will be produced by subject and visit. Only subjects that show suicidal ideation/behavior or self-injurious behavior without suicidal intent will be reviewed (i.e., if a subject's answers are all 'no' for the C-SSRS, then that subject will not be displayed). However, if a subject reported any suicidal ideation/ behavior or self-injurious behavior without suicidal intent at any time point then all their ideation and behavior will be reviewed, even if not positive.

HADS item scores will be listed for subjects with HADS depression subscale ≥ 11 at any time.

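### The primary PK model has a random subject effect that cannot be separated from the residual in a single-dose parallel study (minor; ratios and standard errors unaffected)

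*SAP*

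**What the plan says.** SAP 9.3.2 states that the three log-transformed primary PK parameters "will be evaluated in a linear mixed-effects model with a fixed effect for formulation and a random effect for subject". Treatment differences are then back-transformed to ratios of geometric means with 90% confidence intervals. The example SAS code follows the prose. It runs by parameter, declares "class formulation subject" and includes "random intercept / subject=subject". Protocol 10.3.2.2 describes the same model, and the Statistical Analysis part of the Protocol synopsis says that the parameters "will be evaluated in a linear mixed-effects model with fixed effects for formulation, and a random effect for subject".

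On the design, Protocol 5.1 says that "subjects will receive a single SC dose of one of the following treatments", and Protocol 5.4 explains that "A parallel-group design is chosen because a crossover design is impractical for ixekizumab". SAP section 7 gives the numbers: "Up to 99 subjects may be enrolled to ensure that 78 subjects (26 for each treatment) complete the study". SAP section 12 reports no departure from the protocol's analyses, so the model is not corrected elsewhere.

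**The concern.** A random subject effect belongs in an analysis where subjects contribute more than one value, as in a crossover, because the repeated values allow between-subject variation to be told apart from residual variation. Here each subject receives one formulation once and supplies one Cmax, one AUC(0-∞) and one AUC(0-tlast). With a separate fit for each parameter, subject and record are the same thing.

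The planned primary inference is six 90% intervals: 3 parameters × 2 test formulations against Reference. The model behind them should match the design, and its error degrees of freedom should follow from it without ambiguity. As written, the model contains a term that the data cannot inform, and the degrees of freedom depend on whether that term is counted.

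**Working it through.** **Inputs**
- One dose and one formulation per subject: Protocol 5.1 and 5.4, SAP section 5.
- One fit per parameter, formulation fixed, subject random: SAP 9.3.2.
- Three formulations; 26 per arm, 3 × 26 = 78 completers; at most 99 enrolled, 99/3 = 33 per arm: SAP section 7.
- The documents state no degrees of freedom and no between-subject CV for this analysis, so there is no figure of the plan's own to reproduce.

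**Step 1: the variance structure.** For subject i on formulation f,

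y_i = μ_f + b_i + e_i, with Var(b_i) = σ_b² and Var(e_i) = σ_e².

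With one record per subject, the random-effects design matrix Z is the N × N identity. Hence

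V = σ_b² ZZ′ + σ_e² I = (σ_b² + σ_e²) I.

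Only the sum appears, so any split of the total variance gives the same likelihood.

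**Step 2: the estimates.** Because V is a multiple of the identity, generalised least squares reduces to ordinary least squares. Each formulation difference is a difference of arm means on the log scale, with standard error s√(1/n₁ + 1/n₂), where s² estimates the sum of the two variances. This is the one-way analysis of variance result.

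**Step 3: numerical check.** One data set was simulated with 26 subjects per arm and an assumed CV of 40%. The CV only sets the scale; the result in Steps 1 and 2 is algebraic and holds for any CV.

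| Share of variance given to subject | REML log-likelihood | Test − Reference (log) | SE |
|---|---|---|---|
| 0% | −29.0419 | 0.01975 | 0.09261 |
| 10% | −29.0419 | 0.01975 | 0.09261 |
| 50% | −29.0419 | 0.01975 | 0.09261 |
| 90% | −29.0419 | 0.01975 | 0.09261 |
| 99.9% | −29.0419 | 0.01975 | 0.09261 |

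The one-way analysis of variance SE on the same data is also 0.09261. The REML information matrix for (σ_b², σ_e²) has rank 1 and determinant 0, so the two components are not separately estimable.

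**Step 4: degrees of freedom.** X holds the intercept and three formulation indicators.

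| N | rank X | rank [X Z] | N − rank X | N − rank [X Z] |
|---|---|---|---|---|
| 78 | 3 | 78 | 75 | 0 |
| 99 | 3 | 99 | 96 | 0 |

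The formulation-only model therefore has N − 3 residual degrees of freedom: 75 with t(0.95) = 1.665 at N = 78, and 96 with t(0.95) = 1.661 at N = 99. A residual count that includes the subject term gives 0 at any N, and no finite t interval exists on 0 degrees of freedom. A Satterthwaite calculation with the term kept, using a generalised inverse of the singular information matrix, gives 75.0 and 96.0, in agreement with N − 3. No SAS was run.

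**The case against.** The strongest reply is that nothing in the results moves. The ratios and standard errors are identical with or without the term, and the analysis is framed as estimation of relative bioavailability; the statistical sections state no equivalence margin or pass/fail rule. All of this stands, and it is why the point is minor.

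It can also be said that the code is labelled as an example and that SAP section 3 lets the sponsor and its contractor agree deviations. That gives a route to correction but does not remove the error, because the SAP prose and the protocol specify the same random effect.

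Three stronger readings are tempting, and the documents do not support them.
- *The primary intervals cannot be produced.* This would follow only if the degrees of freedom were computed as N − rank [X Z]. Neither document names that rule, and the software's behaviour was not tested.
- *The absence of a named degrees-of-freedom method is a separate defect.* The SAP does say for the pain model in 9.4.8 that "The Kenward-Roger method will be used to estimate the denominator degrees of freedom", and a reader might set the two side by side. But that model has five correlated time points and an unstructured covariance, where the choice of method matters. Once the subject term is removed, the PK model is one-way and its residual degrees of freedom are simply N − 3.
- *The intervals would be too narrow.* That presumes limits from a normal quantile, which no part of the plan proposes.

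**Conclusion.** The point holds as a minor specification error in the primary analysis. The random subject effect in SAP 9.3.2, Protocol 10.3.2.2 and the Protocol synopsis is fully confounded with the residual. There is no bias and no change to the ratios or their standard errors. What the term does is leave the model mismatched to the design and the degrees of freedom open to a count of zero, where N − 3 is available without any difficulty.

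The confounding rests only on there being one record per subject per fit, which the design and the code establish. That the t distribution on N − 3 degrees of freedom is exact further assumes normal errors with equal variance across arms on the log scale. The values 75 and 96 are illustrations at the completer target and at maximum enrolment. The N in each fit is the number of subjects evaluable for that parameter and may differ between parameters, because SAP 9.3.1 allows individual values to be undeterminable or excluded.

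**What to change.** In SAP 9.3.2, replace the model sentence with text such as:

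> Log-transformed Cmax, AUC(0-∞) and AUC(0-tlast) will each be analysed in a linear model with formulation as the only fixed effect. The 90% confidence intervals will use N − 3 residual degrees of freedom, where N is the number of subjects evaluable for that parameter.

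In the example code, delete the RANDOM line and remove subject from the CLASS line; the MODEL line stays as it is. Enter the change in SAP section 12 as a departure from the protocol's model.

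The cost is two sentences, two code lines and one section 12 entry. No protocol amendment is needed for this alone, since SAP section 3 gives the SAP precedence over the protocol's statistical text. The same section requires sign-off before the first subject is dosed. If the SAP is already signed, report the change in the clinical study report as an agreed deviation. A late correction opens no data-driven choice: the ratios and standard errors do not change, and the degrees of freedom depend only on N.

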10.3.2.2. Pharmacokinetic Statistical Inference

Pharmacokinetic parameters will be evaluated to estimate the relative bioavailability of Test Formulation 1 and Test Formulation 2 compared to the commercial formulation (Reference). Log-transformed C_{\max} and AUC parameters will be evaluated in a linear mixed-effects model with a fixed effect for formulation and a random effect for subject. The treatment differences will be back-transformed to present the ratios of geometric means and the corresponding 90% CI.

The t_{\max} will be analyzed using a Wilcoxon rank sum test. Estimates of the median difference based on the observed medians, 90% CIs and p-values from the Wilcoxon rank sum test will be calculated.

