5. STUDY DESIGN

Study I1F-MC-RHCT is a Phase 1, subject-blind, 3-arm, randomized, parallel-design study in healthy subjects.

Eligible subjects will be admitted to the clinical research unit (CRU) on Day -1 and randomized 1:1:1 to 1 of 3 possible treatments. On Day 1, subjects will receive a single SC dose of one of the following treatments, according to the randomization schedule:

- 80 mg ixekizumab Commercial Formulation (Reference)
- 80 mg ixekizumab Test Formulation 1
- 80 mg ixekizumab Test Formulation 2

Subjects may be allowed to leave the CRU after completing the 4-hour safety assessments on Day 1, at the investigator's discretion, and will return for PK and immunogenicity sampling and safety assessments at predefined times up to 12 weeks postdose.

[figure not shown]

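### The primary PK model gives all three formulations one common variance, so if their between-subject variances differ, at least one test/Reference 90% CI misses nominal coverage

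*SAP*

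**What the plan says.** SAP section 5 describes a "subject-blind, 3-arm, randomized, parallel-design study in healthy subjects", with subjects "randomized 1:1:1 to 1 of 3 possible treatments". Each subject receives a single dose, so each has one Cmax and one value of each AUC. SAP section 7 sets the size: "Up to 99 subjects may be enrolled to ensure that 78 subjects (26 for each treatment) complete the study".

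Under SAP 9.3.2 the log-transformed primary parameters are "evaluated in a linear mixed-effects model with a fixed effect for formulation and a random effect for subject". The example code has "model log_pk = formulation / residual" for the fixed part, "random intercept / subject=subject" for the covariance part, and "lsmeans formulation / alpha=0.1 cl pdiff" for the intervals. There is no REPEATED statement, no GROUP= option and no denominator degrees-of-freedom method.

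Protocol 10.3.2.2 specifies the same model and the same output: "The treatment differences will be back-transformed to present the ratios of geometric means and the corresponding 90% CI".

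Neither document gives an expected CV, states or checks equal variances across formulations, or offers a fallback for this model. SAP 9.1 has geometric CV% reported, but ties nothing to it. The provision to explore other covariance matrices (SAP 9.4.8) applies only to the VAS pain model.

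**The concern.** The two ratios and their 90% CIs are the inferential result for the primary objective, and both come from the same pooled variance. The precision reported for Test 1 against Reference thus depends partly on how variable Test 2 is, and the reverse. Protocol 3.1 says the new formulations change the buffer and tonicity agent. Whether that alters exposure is the study question, and it could also alter how much absorption varies between subjects. If one test formulation were more erratic than the other two arms, the CI of the steadier one would be too wide and its own would be too narrow.

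Equal arm sizes do not remove this. With two equal arms, the pooled standard error of the difference equals the unequal-variance one. Once a third arm is pooled in, that no longer holds.

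**Working it through.** **No plan figure to reproduce.** The 26 per arm comes with no CV, power, precision target or equivalence limits, so it cannot be re-derived.

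**Inputs.** From the documents: three independent arms, n = 26 completers each, one value per subject, two-sided 90% CI. Assumed: between-subject CVs; lognormal data; 75 degrees of freedom (78 − 3) for the pooled interval, because the code names no method.

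**Step 1: the random intercept adds nothing.** With one value per subject, the variance of each observation is subject variance plus residual variance, and only the sum is identified. On a simulated data set of 78 values, the REML log-likelihood was 38.6239 for each of the (subject, residual) pairs (0.01, 0.08), (0.08, 0.01) and (0.045, 0.045), all summing to 0.09. The fit is therefore a one-way analysis with one common variance.

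**Step 2: formulas.** Let v = ln(1 + CV²).

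- Pooled variance: v_p = (v_R + v_T1 + v_T2)/3
- Model SE = √(2·v_p/26)
- Correct SE for test T = √((v_R + v_T)/26)

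The Test 1/Reference SE is right only if v_T2 = (v_R + v_T1)/2, and the Test 2/Reference SE only if v_T1 = (v_R + v_T2)/2. Subtracting the second from the first gives v_T2 − v_T1 = (v_T1 − v_T2)/2, so v_T1 = v_T2, and then both equal v_R. Both intervals are right only if all three variances are equal.

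**Step 3: the stress case, CVs 30/30/50% (Reference/Test 1/Test 2).**

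- v = 0.0862, 0.0862, 0.2231; v_p = 0.3955/3 = 0.1318
- Model SE = √(2 × 0.1318/26) = 0.1007
- Correct SE, Test 1: √(0.1724/26) = 0.0814; ratio 1.237
- Correct SE, Test 2: √(0.3093/26) = 0.1091; ratio 0.923

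**Step 4: simulated coverage of the nominal 90% CI** (60,000 or more trials per scenario):

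| CVs, R/T1/T2 | Test 1: model SE ÷ correct SE | Test 1 coverage | Test 2: model SE ÷ correct SE | Test 2 coverage |
|---|---|---|---|---|
| 30/30/30% | 1.000 | 90.0% | 1.000 | 90.0% |
| 30/30/35% | 1.055 | about 92% | 0.975 | about 89% |
| 30/30/40% | 1.114 | about 93% | 0.955 | about 88.5% |
| 30/30/50% | 1.237 | 95.7% | 0.923 | 87.2% |
| 30/30/20% | 0.905 | 86.4% | 1.061 | 91.8% |

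Unequal-variance (Welch) intervals stayed within 89.6% to 90.4% throughout.

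**Step 5: on the ratio scale.** Hold Reference and Test 1 at 30% and move only Test 2 from 20% to 50%. The median Test 1/Reference CI factor goes from ×/÷1.130 to ×/÷1.181, while the unequal-variance factor stays at ×/÷1.145. In the 50% case the Test 2/Reference factor is ×/÷1.181 pooled and ×/÷1.199 with its own variance.

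**Step 6: cost if variances are equal.** The Welch interval has about 50 degrees of freedom instead of 75. The 95th percentiles of t are 1.676 and 1.665, a ratio of 1.006. The simulated difference in log-scale width was about 0.5%.

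**The case against.** The strongest reply is that the variances may well be close. All arms share the antibody, dose, route, injection region and type of syringe, and subjects are randomized from one healthy population. Variation due to the subjects themselves is common to the arms in expectation, and only formulation-specific absorption can separate them. The 30/30/50% case needs Test 2 to have 0.2231/0.0862 = 2.6 times the log-variance of the others, which is an added component of about 38% CV. This stands. It makes 30/30/50% a stress case, and at close CVs the loss is one or two points of coverage.

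It is also true that reported geometric CVs would show a large gap, that SAP section 3 allows supplementary analyses, and that the code is labelled as an example. But the accompanying text describes the same model, and a variance model chosen after the CVs are seen is post hoc.

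Three stronger readings are tempting, and the documents support none of them:

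- **Both intervals are wrong whenever the CVs differ.** At 30/50/40.9% the Test 2 variance equals the mean of the other two (0.1547), and the Test 1 interval has nominal coverage. The Test 2 ratio is then 1.133.
- **A formulation would be wrongly accepted or rejected.** The stated aim is estimation, and no equivalence limits are given.
- **The `/ residual` option causes the pooling.** It does not. The cause is the missing grouping of the variance.

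**Conclusion.** The point holds as a conditional weakness in the primary analysis. One common variance feeds both test/Reference intervals, and unless all three between-subject variances are equal, at least one interval misses 90% coverage. The size rests on CVs that the documents do not give. It is small for close CVs, moderate at 30/30/40%, and reaches 95.7% and 87.2% only in the stress case. The figures also assume lognormal data, 26 per arm and 75 degrees of freedom for the pooled interval. Since the code leaves the degrees-of-freedom method open, the software's own value may differ.

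A reader might infer that the formulations are known to differ in variability. Nothing in either document shows that they do or that they do not. The effect is on the reported precision of the primary ratios. The estimates themselves are unchanged. This is a worthwhile, cheap improvement, and it does not invalidate the analysis.

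**What to change.** In the SAP 9.3.2 code:

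- Replace "random intercept / subject=subject" with `repeated / group=formulation`.
- Add `ddfm=satterthwaite` to the MODEL statement.

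Welch 90% CIs for each test against Reference are equivalent. Amend the descriptive sentence in 9.3.2 to match.

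The RANDOM line has to go. Kept beside GROUP=, it gives four variance parameters for three identifiable variances. In a check, the REML objective was identical (−86.7698) for subject variances of 0, 0.02, 0.05 and 0.08 with the group residuals adjusted to match.

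Dropping the random subject effect departs from Protocol 10.3.2.2, so SAP 12, which now reports no changes, needs an entry. The choice should be fixed before any PK data are viewed by treatment, because Protocol 10.3.4 and SAP 10 allow PK review during the study.

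The cost is two code edits, one sentence and one SAP 12 entry, plus log-scale CIs about 0.5% wider if the variances are in fact equal.

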	-28 to -2 days prior to Day 1	-1	1	3	5 ±1d	8 ±1d	11 ±1d	15 ±2d	22 ±2d	29 ±2d	36 ±2d	43 ±2d	50 ±2d	57 ±3d	64 ± 3d	71 ±3d	85/ED ±3d	
Administration																		allowed) from 1 hour before until 1 hour after dosing.
Injection-Site Assessments (minutes)			0, 10, 20, 30, 60, 120, 240	X		X												Assessments of induration, swelling, pruritus, and erythema/redness (collected as described in Section 9.4.5.1). 0-minute time point should be done within ± 1 minute following injection; within ± 2 minutes of the 10, 20, and 30-minute time points; within ± 5 minutes of the 60, 120, and 240-minute time points.
Injection-site Bleeding/Bruising Assessment (minutes)			0, 10, 20, 30, 60, 120, 240	X		X												Observational assessment of injection-site bleeding and bruising. 0-minute time point should be done within ± 1 minute following injection; within ± 2 minutes of the 10, 20, and 30-minute time points; within ± 5 minutes of the 60, 120, and 240-minute time points.
Injection-site Pain Assessments using VAS (minutes)			0, 10, 20, 30, 60															Assessment of injection-site pain (VAS) at the 0-minute time point should be done within ± 1 minute following injection; within ± 2 minutes of the 10, 20, and 30-minute time points; within ± 5 minutes of the 60-minute time point.

Procedure	Screening	Days																Comments
	-28 to -2 days prior to Day 1	-1	1	3	5 ±1d	8 ±1d	11 ±1d	15 ±2d	22 ±2d	29 ±2d	36 ±2d	43 ±2d	50 ±2d	57 ±3d	64 ± 3d	71 ±3d	85/ED ±3d	
Ixekizumab PK sample			P	X	X	X	X	X	X	X		X		X		X	X	
Immunogenicity Sample			P					X	X								X	
Pharmacogenetic Sample		X																
Adverse Events and Concomitant Medication	X	X	X	X	X	X	X	X	X	X	X	X	X	X	X	X	X	

Abbreviations: BMI = body mass index; CRU = clinical research unit; C-SSRS – Columbia Suicide Severity Rating Scale; ECG = electrocardiogram; ED = early discontinuation; FSH = follicle-stimulating hormone; ISR = injection-site reaction; P = predose; PK = pharmacokinetics; TB = tuberculosis; TST = tuberculin skin test; VAS = visual analog scale.

3. Introduction

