9.3 Pharmacokinetic Assessment

9.3.1 Pharmacokinetic Analysis

The PK parameter estimates will be determined using non-compartmental methods in validated software program, Phoenix WinNonlin (Certara, Version 6.4 or later):

Serum concentrations of ixekizumab and will be used to determine the following PK parameters, when possible:

Parameter	Units	Definition
AUC(0-∞)	ug.day/mL	area under the concentration versus time curve from time zero to infinity
AUC(0-t _{last})	ug.day/mL	area under the concentration versus time curve from time zero to time t, where t is the last time point with a measurable concentration
%AUC(t _{last} -∞)	%	percentage of AUC that is due to extrapolation from the last measurable concentration to infinity
C _{max}	ug/mL	maximum observed drug concentration
t _{max}	day	time of maximum observed drug concentration
t _{1/2}	day	half-life associated with the terminal rate constant (λ_z) in non-compartmental analysis
CL/F	L/h	apparent total body clearance of drug calculated after extra-vascular administration
V _{ss} /F	L	apparent volume of distribution at steady state after extra-vascular administration
V _z /F	L	apparent volume of distribution during the terminal phase after extra-vascular administration

Weight normalized PK parameters will be calculated. Additional PK parameters may be calculated where appropriate.

Any exceptions or special handling of data will be clearly documented within the final study report.

PK analysis will, where possible, be carried out using actual postdose times recorded in the raw data.

Formatting of tables, figures and abbreviations will follow the Eli Lilly Global PK/PD/TS Tool: NON-COMPARTMENTAL PHARMACOKINETIC STYLE GUIDE. The version of the tool effective at the time of PK analysis will be followed.

General PK Parameter Rules

- Actual sampling times will be used in the final analyses of individual PK parameters, except for non-bolus pre-dose sampling times which will be set to zero.
- C_{max} and t_{max} will be reported from observed values. If C_{max} occurs at more than one time point, t_{max} will be assigned to the first occurrence of C_{max}.
- AUC parameters will be calculated using a combination of the linear and logarithmic trapezoidal methods (linear-log trapezoidal rule). The linear trapezoidal method will be applied up to t_{max} and then the logarithmic trapezoidal method will be used after t_{max}. The

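### The t_max difference is estimated from observed medians but paired with a Wilcoxon 90% CI that belongs to the Hodges-Lehmann shift, so estimate and interval can conflict

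*SAP*

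**What the plan says.** SAP 9.3.2 states that t_max "will be analyzed using a Wilcoxon rank sum test", and continues: "Estimates of the median difference based on the observed medians, 90% CIs and p-values from the Wilcoxon rank sum test will be calculated". Protocol 10.3.2.2 has the same sentence. The estimator is therefore named, not left open. Neither document mentions the Hodges-Lehmann estimate, says how the interval is built or how ties are handled, or gives code for t_max; the example code in SAP 9.3.2 covers only the log-transformed parameters.

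Each comparison is between two independent groups: subjects are "randomized 1:1:1 to 1 of 3 possible treatments" in a parallel design. SAP 9.3.1 says that C_max and t_max "will be reported from observed values", so t_max is always the time of a collected sample. It also says: "Actual sampling times will be used in the final analyses of individual PK parameters".

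Protocol 10.3.2.1 names C_max and the two AUCs as primary and places t_max among other parameters that may be reported. t_max appears in no objective or endpoint in Protocol Section 4.

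**The concern.** Inverting the two-sample rank sum test gives a confidence interval for a location shift. The point estimate that belongs to it is the Hodges-Lehmann estimate, which lies inside the interval by construction. The difference of the two sample medians is another statistic and carries no such guarantee.

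The sampling scheme turns this into a visible problem. Few visits fall near the peak, so a sample median can move by two or three days when one or two subjects shift from one visit to the next. The rank sum test and its interval react much less. The report could then show a difference of several days outside its own 90% CI, or no difference beside a small p-value, and the reader could not tell which figure to believe. What is at stake is the clarity of one supportive comparison.

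**Working it through.** The plan states no t_max effect, SD or power, so there is no figure to reproduce.

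**Inputs**
- 26 per arm. SAP 7: "Up to 99 subjects may be enrolled to ensure that 78 subjects (26 for each treatment) complete the study".
- Visits: the row "Ixekizumab PK sample" in the Schedule of Activities (Protocol Section 2) has post-dose samples on study Days 3, 5, 8, 11, 15, 22, 29 and later. Dosing is on Day 1, so these are 2, 4, 7, 10, 14, 21 and 28 days postdose.
- Visit windows: none stated for Day 3, ±1 day for Days 5 to 11, ±2 days for Days 15 to 29.
- The t_max distribution is not in the documents and is assumed below.

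**Interval.** Sort the 26 × 26 = 676 pairwise differences (test minus reference). With the normal approximation, the rank is C = floor(676/2 − 1.645 × √(26 × 26 × 53/12)) = floor(338 − 1.645 × 54.64) = 248. The 90% CI runs from the 248th smallest difference to the 248th largest, which is the 429th smallest. The Hodges-Lehmann estimate is the mean of the 338th and 339th.

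**Example 1: estimate outside its CI** (nominal times)
- Reference: 14 subjects at 4 days, 12 at 7. Test: 12 at 4, 14 at 7.
- Medians are 4 and 7, so the planned estimate is +3 days.
- Differences: −3 in 12 × 12 = 144 pairs, 0 in 12 × 14 + 14 × 12 = 336, +3 in 14 × 14 = 196.
- Sorted positions 145 to 480 are all 0. Hodges-Lehmann is 0, the CI is (0, 0) and p = 0.59.

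**Example 2: zero estimate beside a small p-value** (nominal times)
- Reference: 4 subjects at 2 days, 20 at 4, 2 at 7. Test: 14 at 4, 8 at 7, 4 at 10.
- Both medians are 4, so the planned estimate is 0.
- Differences: −3 in 28 pairs, 0 in 296, +2 in 56, +3 in 168, larger in 128. Cumulative counts are 28, 324, 380, 548, 676.
- Hodges-Lehmann is 2 days, the CI is (0, 3) and p = 0.0005.

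**How often.** For each assumed distribution, 4,000 two-arm comparisons were simulated with nominal times and with two models of actual times: (a) normal scatter with SD one third of the visit window (window set to 0.05 day for Day 3); (b) whole-day shifts across the window plus up to 0.1 day either way. The table shows the share with the difference of medians outside the 90% CI.

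| Assumed % at 2/4/7/10/14 days | Nominal | Actual (a) | Actual (b) |
|---|---|---|---|
| Both arms 25/35/25/10/5 | 3.2% | 5.6% | 1.7% |
| Reference as above, Test 15/30/30/15/10 | 3.7% | 6.1% | 1.4% |
| Reference 5/65/25/5/0, Test 40/8/12/20/15 (5 at 21 days) | 1.3% | 10.6% | 13.3% |
| Both arms 48/0/42/10/0 | 44.4% | 58.4% | 54.8% |
| Both arms 50/50/0/0/0 | 50.1% | 63.4% | 24.6% |

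The last two rows deliberately put the median at the boundary between two occupied visits. Runs with other assumed equal-arm distributions gave 0.2% to 0.4% with a clear central visit, 4% to 12% with a broader spread, and 22% to 31% at a boundary.

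With actual times, the planned estimate and Hodges-Lehmann had opposite signs in 7% to 16% of comparisons. An estimate of exactly zero with p < 0.10 occurred in 0% to 2.5% with nominal times and not at all with actual times. At most a modest shift in location was simulated, so this says little about a strong one.

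**The case against.** Four points can fairly be made on the other side.

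- **Grammar.** The phrase naming the Wilcoxon test could attach to the p-values alone. The CI method is then unspecified, and the table shells, which are not public, might settle it. This is possible but less natural, and the same sentence would still need the same repair.
- **Same parameter.** Under a pure location shift, the difference of population medians equals the shift, so both statistics aim at one quantity. That stands, and it would be too strong to say that the interval always targets something else. The sample values still part company: four of the five scenarios simulate identical arms or a modest change between arms, and conflicts occur in all of them.
- **Actual times.** SAP 9.3.1 uses actual times, which break ties. This removes exact zeros, but the table shows that it does not reliably lower the share outside the CI.
- **Importance.** t_max is not an endpoint, and no acceptance limit uses it. This stands in full. A reader might infer that the comparison of absorption rate becomes uninterpretable. The documents do not support that: C_max, a primary parameter that also reflects absorption rate, has its own geometric mean ratio and 90% CI.

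**Conclusion.** The mismatch is real and lies in the stated method. The examples prove that estimate and interval can contradict each other at the planned sample size. The frequency is uncertain: about 0% to 6% of comparisons when the median is clearly on one visit, about 20% to 60% when it falls between two visits, and values in between when t_max is spread out or the arms differ in shape. These figures depend on assumed distributions and on the normal-approximation rank. A reader might take the upper figures as the expected rate, but nothing in the documents favours them.

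The consequence is limited to a supportive row of the pharmacokinetic tables. The primary C_max and AUC ratios and their 90% CIs do not change.

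**What to change.** Replace the sentence in SAP 9.3.2 and Protocol 10.3.2.2 with wording such as: *The shift in t_max (test minus reference) will be estimated by the Hodges-Lehmann estimate with its 90% CI from the Wilcoxon rank sum procedure, using actual sampling times. Arm medians and ranges will be presented descriptively.* State whether the CI is exact or asymptotic and how ties are handled.

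The cost is one sentence in each document, a software option and a table label; no new data are needed. If the protocol is not reopened, SAP Section 3 lets the SAP govern, and SAP Section 12, which now reports no changes, should list this one.

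There is a small downside. With heavy ties, the Hodges-Lehmann CI can have zero width, as in Example 1, or touch zero beside a small p-value, as in Example 2. In the simulations, p < 0.10 with a CI that included zero occurred in 10% to 33% of comparisons with nominal times and in 0.3% to 0.8% with actual times. The wording should therefore name actual times, which SAP 9.3.1 already requires.
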